In the model, visit will be treated as a class variable, and an unstructured covariance matrix will be assumed to model the within-subject variability. This model imposes no assumptions on the correlational structure and is considered robust. If there is a convergence problem due to the unstructured covariance matrix, the unstructured covariance matrix will be replaced by compound symmetry in the primary analysis. Denominator degrees of freedom for the *F*-test for fixed effects will be estimated using the Kenward-Roger approximation.⁶⁵ With a mixed-effects model as the primary analysis model based on restricted maximum likelihood estimation and assuming that conditional on fixed and random effects, when data are missing at random, no imputation of missing data will be done.

Additional modeling for LCI and ppFEV₁ and similar analyses may be conducted for other continuous variables. Details will be provided in the SAP.

Pulmonary exacerbation-related endpoints will be analyzed based on 109FAS for the active dosing period and separately for the placebo-controlled period for subjects randomized to placebo group in Study 109.

Number of Pulmonary Exacerbations (Subjects From Study 109 Only)

The number of pulmonary exacerbations, both on-treatment events and events after treatment discontinuation, will be analyzed based on 109FAS using a negative binomial regression model. The model will include treatment, weight (<25 kg versus ≥25 kg) and ppFEV₁ severity (<90 versus ≥90), both as determined at screening in Study 109. The data during the placebo-controlled period for subjects randomized to the placebo group in Study 109 will be analyzed using a similar negative binomial regression model without the treatment in the model.

The annualized rate of pulmonary exacerbation, defined as number of pulmonary exacerbations divided by total exposure, will be summarized and plotted using boxplot.

To further examine whether the treatment effect on pulmonary exacerbation was maintained over time, the annualized event-rate, separately for the previous study (Study 109) and the current study (Study 110), will be provided by treatment arm.

Event of Pulmonary Exacerbation (Subjects From Study 109 Only)

The summary statistics including number of subjects (n) and percent will be provided. A bar chart of incidence of pulmonary exacerbations will be provided.

Time-to-First Pulmonary Exacerbation (Subjects From Study 109 Only)

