10.3.2.2 Analysis of Secondary Endpoints

10.3.2.2.1 Analysis of Secondary Endpoints

The analysis of secondary efficacy endpoints will be conducted for the Treatment Cohort Period 1 only.

Absolute change from baseline in LCI_{2.5}

The analysis for efficacy endpoints will be focused on within-group comparison and summaries. No between-groups comparisons will be performed.

For Treatment Cohort Period 1, the mixed model repeated measures (MMRM) analysis will be used for the Cumulative Study Period based on the FAS. It will include two treatment groups (L200/I-L/I and P-L/I) using baseline of the Previous Study Period.

The absolute change from previous study baseline (including all measurements at each visit, both on-treatment measurements and measurements after treatment discontinuation), will be included as the dependent variable; treatment group, visit, and treatment-by-visit interaction, as fixed effects; and subject as a random effect with adjustment for previous studies (Study 109 versus Study 011B), weight (<25 kg versus \geq 25 kg), and ppFEV₁ severity (<90 versus \geq 90), both as determined at screening in the previous studies, and previous study baseline LCI_{2.5} as a continuous variable.

In the model, visit will be treated as a class variable, and an unstructured covariance matrix will be assumed to model the within-subject variability. This model imposes no assumptions on the correlational structure and is considered robust. If there is a convergence problem due to the unstructured covariance matrix, the unstructured covariance matrix will be replaced by compound symmetry in the primary analysis. Denominator degrees of freedom for the *F*-test for fixed effects will be estimated using the Kenward-Roger approximation.¹ With a mixed-effects model as the primary analysis model based on restricted maximum likelihood estimation and assuming that conditional on fixed and random effects data are missing at random, no imputation of missing data will be done.

The result obtained from the model will be the treatment effect at each post baseline visit. The estimated mean within-group treatment effect, i.e., Least Square (LS) Means, SE, 95% CI, and a 2-sided within treatment group *P* value, will be provided. The LS means of absolute change from previous study baseline with 95% CI at each visit during the Cumulative Study Period will be plotted by treatment groups (L200/I-L/I and P-L/I).

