Appendix D Analysis Visit Window Mapping Rules for Efficacy and Safety Measurements

Table 13-5 Visit Window Mapping Rules for Study 110 Visits

Assessments	Study 110 Visit	Target Study Day	Visit Window (in Study Days)	
• Spirometry (see special handling below)	110 Day 15	15	(1, 22]	
	110 Week 4	29	[23, 43]	
	• Weight and height	110 Week 8	57	[44, 85]
		110 Week 16	113	[86, 141]
	• Vital Signs	110 Week 24	169	[142, 211]
		110 Week 36	253	[212, 295]
		110 Week 48	337	[296, 379]
		110 Week 60	421	[380, 463]
		110 Week 72	505	[464, 547]
		110 Week 84	589	[548, 631]
110 Week 96		673	[632, 687]	
110 Follow-up	701	Nominal Visit		
• Labs	110 Day 15	15	(1, 22]	
	○ Chemistry (Except LFT)	29	[23, 43]	
	○ Hematology	57	[44, 85]	
	110 Week 16	113	[86, 141]	
	110 Week 24	169	[142, 211]	
	110 Week 36	253	[212, 295]	
	110 Week 48	337	[296, 421]	
	110 Week 72	505	[422, 589]	
	110 Week 96	673	[590, 687]	
	110 Follow-up	701	Nominal Visit	
• Chemistry (LFT)	110 Day 15	15	(1, 22]	
	110 Week 4	29	[23, 43]	
	110 Week 8	57	[44, 71]	
	110 Week 12	85	[72, 99]	
	110 Week 16	113	[100, 127]	
	110 Week 20	141	[128, 155]	
	110 Week 24	169	[156, 211]	
	110 Week 36	253	[212, 295]	
	110 Week 48	337	[296, 379]	
	110 Week 60	421	[380, 463]	
	110 Week 72	505	[464, 547]	
	110 Week 84	589	[548, 631]	
	110 Week 96	673	[632, 687]	
110 Follow-up	701	Nominal Visit		
• Coagulation	110 Day 15	15	(1, 22]	
• CFQR, TSQM	110 Week 4	29	[23, 71]	
	110 Week 16	113	[72, 141]	

• TSQM	110 Week 24	169	[142, 253]
	110 Week 48	337	[254, 505]
	110 Week 96	673	[506, 687]
	110 Follow-up	701	Nominal Visit
• Urinalysis (including urine microscopy)	110 Week 16	113	(1, 141]
	110 Week 24	169	[142, 253]
	110 Week 48	337	[254, 505]
	110 Week 96	673	[506, 687]
	110 Follow-up	701	Nominal Visit
• Ophthalmologic examination	110 Week 48	337	[254, 505]
	110 Week 96	673	[506, 687]
	110 Follow-up	701	Nominal Visit
• Standard ECG	110 Day 15	15	(1, 22]
	110 Week 4	29	[23, 43]
	110 Week 8	57	[44, 85]
	110 Week 16	113	[86, 141]
	110 Week 24	169	[142, 253]
	110 Week 48	337	[254, 421]
	110 Week 72	505	[422, 589]
	110 Week 96	673	[590, 687]
	110 Follow-up	701	Nominal Visit
• Sweat Chloride	110 Day 15	15	(1, 22]
	110 Week 4	29	[23, 99]
	110 Week 24	169	[100, 421]
	110 Week 96	673	[422, 687]
• LCI	110 Day 15	15	(1, 22]
	110 Week 4	29	[23, 99]
	110 Week 24	169	[100, 253]
	110 Week 48	337	[254, 505]
	110 Week 96	673	[506, 687]

Special handling for spirometry assessments:

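### The MMRM pairs a redundant random subject effect with an unstructured matrix and has only compound symmetry as a fallback, which could understate late-visit standard errors if it is used

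*SAP*

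**What the plan says.** SAP 10.3.2.2.1 describes the MMRM for change in LCI2.5 from the previous-study baseline over the Cumulative Study Period. Its covariance specification has four parts:

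- A random effect: "subject as a random effect with adjustment for previous studies (Study 109 versus Study 011B", among other covariates.
- A within-subject matrix in the same model: "an unstructured covariance matrix will be assumed to model the within-subject variability". The SAP adds: "This model imposes no assumptions on the correlational structure and is considered robust".
- A single fallback on non-convergence: "the unstructured covariance matrix will be replaced by compound symmetry in the primary analysis".
- Denominator degrees of freedom "estimated using the Kenward-Roger approximation". No empirical (sandwich) standard error is mentioned.

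Protocol 12.4.3 has the same random effect, the same matrix and the same rule: "If there is a convergence problem due to the unstructured covariance matrix, the unstructured covariance matrix will be replaced by compound symmetry".

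The model yields within-group least squares means by visit, with standard error, 95% CI and P value; the SAP states "No between-groups comparisons will be performed". SAP 10.3.2.2.1 and 10.3.2.2.2 reuse it for sweat chloride, BMI, CFQ-R, LCI5.0, ppFEV1, weight, height and TSQM. The Study 110 visits come from the table "Visit Window Mapping Rules for Study 110 Visits" in Appendix D: 11 post-baseline treatment visits for spirometry, weight and height, and 5 for LCI.

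**The concern.** Two features work against each other.

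First, an unstructured matrix already contains any variance shared across a subject's visits. A separate random subject variance cannot be told apart from it. A programmer who codes both adds a parameter that cannot be estimated, and this may produce the convergence problem that triggers the fallback.

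Second, the fallback goes in one step from a fully free matrix to two parameters. Homogeneous compound symmetry assumes one variance for all visits, and one correlation whether visits are two weeks or about two years apart. In the P-L/I group it also treats placebo visits and later active-drug visits alike. If the spread of change grows over time, pooling makes early intervals too wide and late ones too narrow. The Week 96 interval is the one that bears most directly on the durability objective.

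**Working it through.** **Figures in the plan.** Neither document gives a standard error, SD by visit, correlation, dropout rate or power for the MMRM. The only design figure is the table of intervals for CF lung incidence (SAP Table 7-1). It reproduces: 0.1 ± 1.96 × √(0.1 × 0.9 / 256) = (0.063, 0.137), and the other three rows also match. It does not bear on this point.

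**Step 1: redundancy.** Count covariance parameters and compare with the rank of the derivative of the marginal covariance matrix.

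- Unstructured at 7 visits: 7 × 8 / 2 = 28. Adding a subject variance gives 29, but the rank is 28, so one parameter is not identifiable.
- Compound symmetry plus a subject variance: 3 parameters, rank 2. The fallback has the same redundancy if the random term is kept.

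**Step 2: size of the matrix.** For p visits: unstructured p(p+1)/2; heterogeneous Toeplitz 2p − 1; heterogeneous AR(1) or heterogeneous compound symmetry p + 1; compound symmetry 2. SAP Table 10-2 shows Day 15 and Week 24 of the previous studies but not the full list. I assume 4 previous-study visits for LCI and 5 for spirometry.

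| Model | Visits | Unstructured | Het. Toeplitz | Het. AR(1) or het. CS | CS |
|---|---|---|---|---|---|
| LCI | 4 + 5 = 9 | 45 | 17 | 10 | 2 |
| ppFEV1 | 5 + 11 = 16 | 136 | 31 | 17 | 2 |

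The 11 Study 110 visits alone need 66. About 256 children are potentially eligible.

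**Step 3: last-visit standard error under compound symmetry, complete data.** Assume the SD of change rises linearly from 1 at Week 2 to r at cumulative Week 120 (24 + 96). The 16 assumed visits are Weeks 2, 4, 8, 16, 24, 26, 28, 32, 40, 48, 60, 72, 84, 96, 108 and 120. With t = (week − 2)/118, the mean of t is 0.3898 and the mean of t² is 0.2487. Then:

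- pooled variance = 1 + 2(r − 1)(0.3898) + (r − 1)²(0.2487)
- SE ratio (model/true) at the last visit = √(pooled variance) / r
- coverage = 2Φ(1.96 × ratio) − 1

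| r | Pooled variance | SE ratio, last visit | Coverage |
|---|---|---|---|
| 0.8 | 0.854 | 1.16 | 97.6% |
| 1.0 | 1.000 | 1.00 | 95.0% |
| 1.25 | 1.210 | 0.88 | 91.5% |
| 1.5 | 1.452 | 0.80 | 88.5% |
| 2.0 | 2.028 | 0.71 | 83.7% |

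The first-visit ratio is √(pooled variance): 1.10, 1.20 and 1.42 for r = 1.25, 1.5 and 2.0, so early intervals are too wide.

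**Step 4: sensitivity.** A large-sample calculation compared the model-based compound-symmetry standard error with the true one for both schedules. True correlation was either constant (0.6) or decaying (0.7 per 24 weeks), and dropout completely at random was 0% or 30%. All are assumptions. Last-visit results over the scenarios:

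| r | SE ratio | Coverage |
|---|---|---|
| 0.8 | 1.01–1.18 | 95.3–97.9% |
| 1.0, complete data or constant correlation | 1.00 | 95.0% |
| 1.0, decaying correlation and 30% dropout | 0.88–0.90 | 91.7–92.2% |
| 1.25 | 0.77–0.88 | 87.1–91.5% |
| 1.5 | 0.70–0.80 | 83.0–88.5% |
| 2.0 | 0.61–0.71 | 76.5–83.7% |

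**Step 5: with a heterogeneous structure.** Each visit keeps its own variance, so with complete data the last-visit ratio is 1.00 by construction.

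**The case against.** A reader might infer that the plan will understate late standard errors. The documents do not support that. Compound symmetry applies only after non-convergence, and no convergence result is reported. The bias also needs a rising SD, or decaying correlation together with late missing data, and the documents quantify none of these. A rising SD is most plausible for raw height and weight change in growing children. It is less obvious for age-adjusted z-scores or for CFQ-R and TSQM scores bounded at 0 and 100.

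A reader might also carry the 136-parameter count over to LCI2.5, for which the model is written. That would be wrong: LCI has 5 Study 110 visits, and 45 parameters on the assumed schedule. The 11-visit schedule applies to ppFEV1, weight, height and BMI.

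The random-effect phrase may be loose wording for the repeated-measures subject. If both terms were coded and the fit converged, the unstructured matrix would absorb the subject variance, and the least squares means and standard errors would not change. Nor is the SAP's robustness sentence false: it describes the unstructured fit and precedes the fallback.

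Materiality is limited. SAP 10.3.2.3 makes all efficacy endpoints secondary with nominal P values. SAP 10.3.2.2.1 also tabulates mean, SD and SE of change by visit, which do not depend on the covariance model, so a Week 96 standard error that was too small could be noticed beside them. The rate-of-change models for LCI and ppFEV1 do not use this fallback.

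All of this stands, and it lowers the importance. It does not remove the gap. The descriptive tables are unadjusted observed-case summaries. Some late missingness is built in, because the FAS includes children never dosed in Study 110. A programmer must still decide what the random-effect phrase means.

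**Conclusion.** The concern holds in a conditional form. Taken literally, the random subject effect is redundant: harmless if the fit converges, but a possible cause of failure. The only fallback is homogeneous compound symmetry with model-based standard errors, and the freedom from correlation assumptions does not carry over to it.

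If the fallback is used, most plausibly in the models with 11 Study 110 visits, late-visit standard errors could be understated. The complete-data figures, 0.88 to 0.71 of the true value for SD ratios of 1.25 to 2.0, are the mild end for a rising SD; decaying correlation with dropout makes them worse. A constant SD with complete data gives no error, and a falling SD errs the other way. The size therefore rests on assumed SD patterns and assumed previous-study visits. Importance is low to moderate: it concerns the intervals for a secondary durability objective, not the primary safety analysis.

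**What to change.** In SAP 10.3.2.2.1:

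1. Delete the random subject effect, or state that the unstructured matrix is the residual (R-side) matrix and that no separate subject term is fitted. Align the missing-data sentence, which also refers to random effects.
2. Replace the single fallback by an ordered list, taking the first structure that converges: unstructured; heterogeneous Toeplitz; heterogeneous AR(1) or heterogeneous compound symmetry; homogeneous compound symmetry last. Keep Kenward-Roger for all but the last. The exact order of the middle steps matters less than having visit-specific variances before compound symmetry.
3. If homogeneous compound symmetry is reached, use empirical standard errors with a compatible degrees-of-freedom method.
4. Limit the robustness sentence to the unstructured fit, and report which structure was used for each endpoint.

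The cost is SAP wording and a few lines of code, with a note that this refines the rule in Protocol 12.4.3. The one technical downside is that empirical standard errors cannot be combined with Kenward-Roger in SAS, so the last step needs its own degrees-of-freedom rule.

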7.3 Other Secondary Endpoints

Treatment Cohort

The following efficacy endpoints will be analyzed using baseline values in the previous study (i.e., Study 109, Study 011B, or Study 011B LCI Substudy):

- Absolute change from baseline in LCI_{5.0} (subjects from Study 109 and the Study 011B LCI Substudy only)
- Absolute change from baseline in percent predicted forced expiratory volume in 1 second (ppFEV₁)
- Relative change from baseline in ppFEV₁
- Absolute change from baseline in BMI-for-age z-score
- Absolute change from baseline in weight
- Absolute change from baseline in weight-for-age z-score
- Absolute change from baseline in height
- Absolute change from baseline in height-for-age z-score

- Absolute change from baseline in Treatment Satisfaction Questionnaire for Medication (TSQM) domains
- Time-to-first pulmonary exacerbation, including pulmonary exacerbations in the previous study and the current study (subjects from Study 109 only)
- Event of having at least 1 pulmonary exacerbation, including pulmonary exacerbations in the previous study and the current study (subjects from Study 109 only)
- Number of pulmonary exacerbations, including pulmonary exacerbations in the previous study and the current study (subjects from Study 109 only)

The following efficacy endpoints will be analyzed using baseline values in the current study (Study 110):

- Absolute change from baseline in LCI_{5.0} (subjects from Study 109 and the Study 011B LCI Substudy only)
- Absolute change from baseline in ppFEV₁
- Relative change from baseline in ppFEV₁
- Absolute change from baseline in BMI-for-age z-score
- Absolute change from baseline in weight
- Absolute change from baseline in weight-for-age z-score
- Absolute change from baseline in height
- Absolute change from baseline in height-for-age z-score
- Absolute change from baseline in TSQM domains
- Time-to-first pulmonary exacerbation in the current study (subjects from Study 109 only)
- Event of having at least 1 pulmonary exacerbation in the current study (subjects from Study 109 only)
- Number of pulmonary exacerbations in the current study (subjects from Study 109 only)

The following efficacy endpoints will also be analyzed:

- Rate of change in LCI_{2.5} (subjects from Study 109 and the Study 011B LCI Substudy only)
- Rate of change in LCI_{5.0} (subjects from Study 109 and the Study 011B LCI Substudy only)
- Rate of change in ppFEV₁

Observational Cohort

Not applicable

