12.4 Statistical Analysis

12.4.1 General Considerations

For the Observational Cohort, summaries will only be provided for the disposition, demographic and baseline characteristics, and SAEs. Summaries will be provided based on all enrolled subjects in that cohort.

For the Treatment Cohort, analyses will be repeated for current dosing period, cumulative dosing period (efficacy only), and active dosing period as shown in Table 12-3. All analyses will be provided using all data, regardless of whether the subjects turn 12 years of age and subsequently switch to LUM 400 mg q12h/IVA 250 mg q12h, to examine the treatment strategy, which includes the age-based dose regimen switch.

Table 12-3 Analysis of Efficacy and Safety in Different Dosing Periods

Period	Efficacy	Safety
Current Dosing Period	X	X
Cumulative Dosing Period	X	None
Active Dosing Period	X	X

- Efficacy analysis (except those related to pulmonary exacerbations, LCI, [REDACTED]) will be based on the FAS for the current dosing period, and based on the IFAS for the cumulative dosing period and the active dosing period.
 - Pulmonary exacerbation-related analysis for the active dosing period will be based on 109FAS by treatment group. The placebo-controlled period for subjects randomized to the placebo arm will be analyzed separately.
 - LCI related analysis will be based on the LCI Analysis Set for the current dosing period, and based on the Integrated LCI Analysis Set for the cumulative dosing period and the active dosing period.

- Safety analysis will be based on the Safety Set for the current dosing period, and based on the Integrated Safety Set for the active dosing period.

All subject data listings for the Treatment Cohort will be referenced using the Integrated All Subjects Set, unless otherwise specified.

Continuous variables will be summarized using the following descriptive summary statistics: the number of subjects (n), mean, standard deviation (SD), median, minimum value, and maximum value.

Categorical variables will be summarized using counts and percentages.

Baseline: The baseline value of each dosing period is defined as the most recent measurement before intake of the first dose of the corresponding dosing period, except if specified otherwise.

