5.2 Secondary Objectives

- To evaluate the long-term efficacy and durability of lumacaftor in combination with ivacaftor for subjects in Treatment Cohort Period 1
- To evaluate the long-term safety of lumacaftor in combination with ivacaftor for subjects in Treatment Cohort Period 2

- To evaluate the post-treatment safety of lumacaftor in combination with ivacaftor for subjects in the Observational Cohort

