6.2 Secondary Endpoints

Treatment Cohort Period 1

The following efficacy endpoints are defined using baseline values in the previous study (i.e., Study 109 or Study 011B):

- Absolute change from baseline in LCI_{2.5} (subjects from Study 109 and Study 011B LCI Substudy only)
- Absolute change from baseline in sweat chloride
- Absolute change from baseline in body mass index (BMI)
- Absolute change from baseline in Cystic Fibrosis Questionnaire – Revised (CFQ-R) respiratory domain score

The following efficacy endpoints are defined using baseline values in the current study (i.e., Study 110):

- Absolute change from baseline in LCI_{2.5} (subjects from Study 109 and Study 011B LCI Substudy only)
- Absolute change from baseline in sweat chloride
- Absolute change from baseline in BMI
- Absolute change from baseline in CFQ-R respiratory domain score

Treatment Cohort Period 2

- Safety, as determined by AEs and serious adverse events (SAEs), liver function tests (LFTs), and ophthalmologic examinations

Observational Cohort

Safety, as determined by SAEs

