8.1 Efficacy Set

Full Analysis Set (FAS) includes all subjects who are randomized and dosed in Study 109, or subjects enrolled and dosed in Study 011B. The FAS treatment group assignment is shown in Table 8-1; the treatment group will be as randomized/enrolled in the previous studies.

Table 8-1 FAS Treatment Group Assignment in Study 110

Treatment Groups	Description
L200/I-L/I	Subjects randomized/enrolled to L200/I in the previous studies (Study 109 or Study 011B) ^a
P-L/I	Subjects randomized to placebo in Study 109 ^a

I: ivacaftor; L: lumacaftor; P: placebo.

^a Subjects who turn 12 years of age in the previous studies or Day 1 of this rollover study will begin receiving L400/I on Day 1. Subjects who turn 12 years of age after the Day 1 Visit of this rollover study will begin receiving L400/I at their next scheduled visit.

110 Full Analysis Set (110 FAS): The 110 FAS will include all subjects who rolled over from Study 109 and Study 011B, and who are enrolled and exposed to any amount of study drug in Study 110. The 110 FAS treatment group assignment is shown in Table 8-2; the treatment group will be as randomized/enrolled in the previous studies.

Table 8-2 110 FAS Treatment Group Assignment in Study 110

Treatment Groups	Description
L200/I-L/I	Subjects randomized/enrolled to L200/I in the previous studies (Study 109 or Study 011B) and enrolled and dosed in Study 110 ^a
P-L/I	Subjects randomized to placebo in Study 109 and enrolled and dosed in Study 110 ^a

I: ivacaftor; L: lumacaftor; P: placebo.

^a Subjects who turn 12 years of age in the previous studies or Day 1 of this rollover study will begin receiving L400/I on Day 1. Subjects who turn 12 years of age after the Day 1 Visit of this rollover study will begin receiving L400/I at their next scheduled visit.

109 Full Analysis Set (109 FAS): The 109 FAS will include all subjects who are randomized and exposed to any amount of study drug in Study 109.

109 Rollover Set (109 ROS): The 109 Rollover Set will include subjects who rolled over from Study 109 (enrolled in Study 110) and were exposed to any amount of study drug in Study 110.

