10.1.1 Efficacy Analysis Presentation Rules and Format

Treatment Cohort Period 1

For all continuous efficacy variables, change from previous study baseline with two treatment groups: L200/I-L/I and P-L/I, will be summarized descriptively and using a mixed model repeated measure (MMRM) model. The presentation format is provided in Table 10-2.

Descriptive summary of raw values and change from current study baseline for P-L/I will also be summarized in separate tables with one column.

Table 10-2 Continuous Efficacy Variable Summary Presentation Format

Summary statistics	109/011B and 110	
	L200/I-L/I	P-L/I
109/011B Baseline	xx	xx
109/011B Day 15	xx	xx
Change at 109/011B Day 15	xx	xx
...
109/011B Week 24	xx	xx
Change at 109/011B Week 24	xx	xx
110 Day 15	xx	xx
Change at 110 Day 15	xx	xx
...

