Raw values and absolute change from previous study baseline, at each visit during the Cumulative Study Period, will be summarized in a separate table. Descriptive statistics, including number of subjects (*n*), mean, SD, SE, median, minimum, and maximum, will be provided.

In addition, descriptive summary statistics will be provided in a separate table for raw values and absolute change from current study baseline for P-L/I for visits in the Current Study Period using 110 FAS, including number of subjects (*n*), mean, SD, SE, median, minimum, and maximum along with the 95% CI based on Normal approximation.

Absolute change from baseline in sweat chloride

The analysis of sweat chloride will be similar to the MMRM analysis described above for LCI_{2.5}, with the absolute change from previous study baseline in sweat chloride at each visit as the dependent variable; and replacing the baseline LCI_{2.5} with baseline sweat chloride of the previous studies as a continuous covariate. Figure for sweat chloride endpoints will be plotted similar to absolute change in LCI_{2.5} above. Descriptive summary based on the current study baseline for P-L/I, similar to the summary of LCI_{2.5}, will be provided separately.

Absolute change from baseline in BMI and BMI-for-age Z-score

The analysis of BMI and BMI-for-age Z-score will be similar to the MMRM analysis described above for LCI_{2.5}, with the absolute change from previous study baseline in BMI or BMI-for-age z-score, respectively, at each visit as the dependent variable; and removing the continuous

covariate baseline LCI_{2.5}. Figure for BMI and BMI-for-age z-score will be plotted similar to absolute change in LCI_{2.5} above. Descriptive summary based on the current study baseline for P-L/I, similar to the summary of LCI_{2.5}, will be provided separately.

Absolute change from baseline in CFQ-R respiratory domain

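### Change from the Study 110 baseline is defined for everyone in Treatment Cohort Period 1 but analysed for P-L/I only, so the longest-treated group has no interval for change during Study 110

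*SAP*

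**What the plan says.** Durability is a secondary objective for the whole treated cohort (SAP 5.2): "To evaluate the long-term efficacy and durability of lumacaftor in combination with ivacaftor for subjects in Treatment Cohort Period 1". SAP 6.2 introduces a block of secondary endpoints with "The following efficacy endpoints are defined using baseline values in the current study (i.e., Study 110", and SAP 6.3 has a parallel block. Neither is limited to a treatment group.

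Protocol 12.4.1 says that efficacy, apart from named exceptions, "will be based on the FAS for the current dosing period, and based on the IFAS for the cumulative dosing period". Protocol 12.2 puts both treatment groups in that FAS, and the LCI Analysis Set, used for LCI, is a subset with both groups as well. Protocol 12.4.3 adds a 95% CI of the mean to the by-visit summaries, without restricting the group.

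The SAP keeps both groups in the 110 FAS. L200/I-L/I is described in SAP 8.1 as "Subjects randomized/enrolled to L200/I in the previous studies (Study 109 or Study 011B) and enrolled and dosed in Study 110", and Table 10-1 assigns the 110 FAS to current-period efficacy. Yet SAP 10.1.1 sets this general rule: "Descriptive summary of raw values and change from current study baseline for P-L/I will also be summarized in separate tables with one column". SAP 10.3.2.2.1 applies it to LCI2.5 ("raw values and absolute change from current study baseline for P-L/I for visits in the Current Study Period using 110 FAS"). The remaining continuous endpoints in 10.3.2.2.1 and 10.3.2.2.2 carry the same P-L/I limit.

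On exacerbations, Protocol 7.3 lists current-study endpoints, such as "Number of pulmonary exacerbations in the current study (subjects from Study 109 only". Protocol 12.4.3 plans annualized rates by arm, separately for Study 109 and Study 110: "To further examine whether the treatment effect on pulmonary exacerbation was maintained over time".

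**The concern.** Whether a benefit is durable has two parts. Is the patient still better than before treatment? Has the early gain held, grown or eroded since? Change from pre-treatment baseline answers the first. The second needs change over the extension period, with its uncertainty, in the children who were already on drug when the extension began. Those children are the L200/I-L/I group, and the SAP gives the extension-period change only for the other group. In P-L/I the same quantity measures the first response to active drug, which is a different question.

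At stake is a stated secondary objective in the group that can reach about 120 weeks on drug (24 in the parent study plus 96 in Study 110). A loss or gain between parent Week 24 and Study 110 Week 96 could be seen as a difference of two reported means, but no interval would show how precisely it was estimated.

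**Working it through.** **The plan's own precision figure.** The only one is SAP Table 7-1, for CF lung incidence at n = 256. It reproduces: 0.1 ± 1.96 × √(0.1 × 0.9 / 256) = 0.1 ± 0.037, giving (0.063, 0.137), and the other three rows also match. It has no bearing on durability, for which no precision is stated.

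**Count of endpoints.** SAP 6.2 lists 4 current-baseline endpoints: LCI2.5, sweat chloride, BMI and CFQ-R respiratory domain. SAP 6.3 lists 9: LCI5.0, absolute and relative ppFEV1, BMI z-score, weight, weight z-score, height, height z-score and TSQM domains. 4 + 9 = 13. Following each into SAP 10.3.2.2.1 and 10.3.2.2.2, all 13 have a P-L/I summary and none has an L200/I-L/I summary.

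**What L200/I-L/I does receive.**
- Repeated-measures LS mean change from the previous-study baseline, with SE, 95% CI and within-group P value, at each visit of the Cumulative Study Period, plus a descriptive table of the same change (SAP 10.3.2.2.1).
- Exacerbation analyses over the Cumulative Study Period, with a model-based CI for the rate (SAP 10.3.2.2.2).
- A share in an annualized slope for LCI2.5, LCI5.0 and ppFEV1. The groups in that model are Placebo and L/I Overall, so no slope belongs to L200/I-L/I alone. Sweat chloride, BMI and CFQ-R have no slope.

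**Can the missing interval be recovered from the by-visit output?** The point estimate can: subtract the two LS means. The interval cannot. With equal standard errors SE at the two visits and correlation ρ between the two estimates,

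Var(Week 96 − Week 24) = 2 × SE² × (1 − ρ),

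so the half-width of the difference is √(2(1 − ρ)) times a single-visit half-width. The documents give no ρ. Over an assumed range:

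| ρ (assumed) | multiple of single-visit half-width |
|---|---|
| 0.3 | 1.18 |
| 0.5 | 1.00 |
| 0.7 | 0.77 |
| 0.9 | 0.45 |

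The extremes differ by a factor of about 2.6 (1.18 / 0.45). The SAP does not plan to report the between-visit covariance, so a reader cannot choose among these values.

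**Why one pooled L200/I-L/I column would not be enough.** Study 011B subjects have a planned washout from Week 24 to Week 26 before Study 110 Day 1 (SAP 7.1). Their change from the Study 110 baseline therefore includes the effect of restarting drug. Most Study 109 subjects start Study 110 on the day of their Week 24 Visit (SAP 9.1.1). The column would mix two kinds of baseline.

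**The case against.** The strongest reply is that durability is already estimated. By-visit change from pre-treatment baseline with a 95% CI, carried through Study 110, shows whether benefit persists, and the SAP does not define durability in any other way. That stands. A reader might infer that the objective has no estimate in the longest-treated group; the documents do not support that. Only the interval for change during Study 110 and a group-specific slope are missing.

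The slope model is also a maintenance analysis that uses all L200/I-L/I follow-up from Week 2. This stands in part: it pools the groups and covers only LCI and ppFEV1.

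Three other stronger readings also go too far.
- That the washout explains the omission. The SAP gives no reason.
- That Study 110 Day 1 is always an on-drug value for active Study 109 children. Some sites have a Roll-Over Gap (SAP 9.1.3), and some subjects may enter while off drug with sponsor approval (Protocol 8.1).
- That the exacerbation split by study has been dropped. SAP 10.3.2.2.2 divides events by exposure in each study period, which can be read as keeping the split. The paragraphs before it pair each group with one period, so the text is ambiguous rather than plainly a departure.

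Finally, the SAP contents show obscured material between 10.3.2.3 and 10.4, and SAP 4 says that additional analyses are included. A further analysis there cannot be excluded, although the general rule in 10.1.1 makes it less likely.

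**Conclusion.** The point holds in this limited form. Thirteen endpoints are defined without group restriction and, in the visible text, analysed for one of two groups. This departs from the protocol's current-period plan. In L200/I-L/I, no visible analysis gives a CI for change during Study 110 or a slope for that group alone.

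The number of children affected cannot be fixed from the documents. The Study 109 allocation is not stated, and 256 is the number potentially eligible, not the number enrolled. The table of multiples rests on assumed correlations and equal standard errors. It shows only that the interval is not recoverable; it does not measure a bias in the plan.

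Efficacy is secondary here and its P values are nominal (SAP 10.3.2.3), so the primary safety objective is untouched. The change should still be made, because it gives a stated objective an interval it otherwise lacks, at very little cost.

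**What to change.** 1. From the cumulative repeated-measures models already planned, report for L200/I-L/I the contrast Study 110 Week 96 minus parent-study Week 24, with 95% CI, for LCI2.5, sweat chloride, BMI and BMI z-score, CFQ-R respiratory domain and ppFEV1. Do this where the measure was taken at parent Week 24, which the parent protocols must confirm. This reference precedes the Study 011B washout and any Roll-Over Gap. If a model falls back to compound symmetry, say so beside the contrast, because its interval then depends on that structure.
2. Tabulate the defined change from the Study 110 baseline for L200/I-L/I, with 95% CI, split by previous study (109 and 011B).
3. State in SAP 10.3.2.2.2 that the annualized exacerbation rate is given by arm, separately for Study 109 and Study 110, as in Protocol 12.4.3.

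The cost is one contrast statement per planned model, extra columns in existing table shells and one clarifying sentence. No new data are needed, and no error rate is affected.
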